4.7.1.2 Day 2 (early ferumoxytol MRI)

The subject will undergo an anatomical MRI of the CNS/body/extremities (brain &/or spine [group1], carotids and/or aorta and/or other arteries or veins [group2] or cervical lymph nodes [group3]) with and without ferumoxytol, which may include DWI, MRA, MRV or perfusion study. Ferumoxytol will be administered intravenously, not exceeding the total dose of 510mg; see sections 4.5 and 5.1. Short abdominal MR imaging will be performed in the subgroup.

4.7.1.3 Day 3 (late ferumoxytol MRI)

Group1: Approximately 24 hours after the ferumoxytol infusion, the subject will have a post-ferumoxytol MRI brain and/or spine, Gadolinium MRI may be repeated at the investigator's discretion based on subject's suspected or known diagnosis. Subjects with renal insufficiency (GFR <50ml/min/1.73m²) and/or contraindication to GBCA, will not receive Gadolinium. Group2 and 3 subjects will undergo MRI of the carotids, aorta or other arteries or veins or cervical lymph nodes respectively approximately 48h after ferumoxytol injection. Short abdominal MR imaging will be performed in the subgroup (24-48 hours after ferumoxytol administration).

4.7.1.4 Day 4 (2nd late ferumoxytol MRI) (at physician's discretion for groups 2 and 3)

Subjects in groups 2 and 3 who undergo vessel imaging or cervical lymph node imaging will repeat the post ferumoxytol MRI approximately 1 week (6-8 days) after the ferumoxytol infusion, at the physician's discretion. Any subject in the abdominal imaging subgroup from groups 1, 2 & 3 will undergo short abdominal MR imaging 1 week after ferumoxytol administration.

4.7.1.5 Body Imaging (to assess for body imaging clearance)

Subgroup subjects will undergo short abdominal MR imaging 1, 2, 3 and 6 months after ferumoxytol infusion to test long term ferumoxytol uptake and clearance from the body. Once no ferumoxytol is detected on the abdominal MR images, no further scanning will be done. (i.e. if ferumoxytol is detected at 1 month, 3 month abdominal scans will be performed. If no ferumoxytol is detected at 3 months, the 6 month scans will not be performed). During this time, subjects that receive additional ferumoxytol will be removed from the subgroup portion of the study. If subject comfort or logistics do not allow for the completion of all post-ferumoxytol abdominal MRI timepoints, it will not exclude the patient from subsequent abdominal scans.

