4.9 Evaluation of Organ Uptake and Clearance of Ferumoxytol

This additional part of the study will evaluate the time needed after ferumoxytol administration before the MR signal in certain organs including the liver, spleen, pancreas and bone marrow returns to a level which allows clinically satisfactory MR imaging of these organs. Various MR sequences will be tested to determine which is the most applicable to reduce confounding effect of prior ferumoxytol administration. Abdominal MR scans will be performed in 50 subjects before and at multiple time points after the first ferumoxytol administration. These subjects will be a subgroup from groups; 1, 2 and 3. The time points will be: before, shortly after, 24-48 h after, 1 week after, 1, 2, 3 and 6 months after ferumoxytol administration. Once signal changes are no longer present, subsequent imaging will not be necessary. The sequences will be short, without full anatomical coverage.

If a subject does not qualify for the abdominal imaging (because of previous iron injection) or chooses not to participate in the abdominal imaging, the subject can still be enrolled in and complete the primary group imaging sessions.

The MRI sequences are detailed in section 5.1.

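### Does stopping abdominal scans at clearance, with no stated rule for counting cleared subjects, bias the estimate of how long ferumoxytol is retained?

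*Combined protocol and SAP*

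**What the plan says.** Section 4.7.1.5 schedules abdominal scans at 1, 2, 3 and 6 months after the infusion, then adds "Once no ferumoxytol is detected on the abdominal MR images, no further scanning will be done". Its example reads "if ferumoxytol is detected at 1 month, 3 month abdominal scans will be performed" and continues "If no ferumoxytol is detected at 3 months, the 6 month scans will not be performed". Section 4.9 repeats the rule: "Once signal changes are no longer present, subsequent imaging will not be necessary".

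Scans can also be absent for two other reasons, both in 4.7.1.5. On re-dosing: "During this time, subjects that receive additional ferumoxytol will be removed from the subgroup portion of the study". On a time point missed for comfort or logistics: "it will not exclude the patient from subsequent abdominal scans".

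Section 4.9 states the aim as the time needed until the signal in the liver, spleen, pancreas and bone marrow "returns to a level which allows clinically satisfactory MR imaging of these organs". On evaluation, section 5.2 says only that abdominal images at the various time points are compared with the baseline scan. Section 6.1 promises descriptive summaries of all outcomes and gives detail for groups 1 to 3, but does not name the abdominal subgroup.

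**The concern.** Whether a later image exists depends on the outcome being measured. A subject who clears early contributes nothing to the later visits, and a subject who clears late contributes to all of them. If the images in hand at 3 or 6 months were simply tabulated, the slow clearers would stand for everyone. The study would then report that ferumoxytol disturbs abdominal MRI for longer than it does, which is the practical question in section 4.9. A scan absent because of clearance means something different from one missed or lost through re-dosing, and no rule separates them.

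**Working it through.** **Inputs.** From the documents: 50 subjects (3.2.3, 4.9); scans at 1, 2, 3 and 6 months (4.7.1.5, 4.9, 5.1.6.5); scanning ends at clearance. The documents give no retention rate, clearance rate or precision for the subgroup, so there is no figure to reproduce. All rates below are assumptions.

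**Direction.** Let S(k) be the true share still showing ferumoxytol at visit k. If clearance is lasting and no scan is otherwise missed, only subjects positive at the previous visit are scanned at visit k. The share positive among acquired scans is then S(k)/S(k−1). This is never below S(k), and it is above S(k) once anyone has cleared and someone is still positive.

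**Size, subject level.** Assumed true shares of 90, 70, 50 and 20%:

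| Month | Scanned | Positive | Among scanned | Of all 50 | Excess (points) |
|---|---|---|---|---|---|
| 1 | 50 | 45 | 90% | 90% | 0 |
| 2 | 45 | 35 | 78% | 70% | 8 |
| 3 | 35 | 25 | 71% | 50% | 21 |
| 6 | 25 | 10 | 40% | 20% | 20 |

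With a slower curve (95, 85, 70, 40%), the 6-month share reads 57% against 40%. With a faster one (70, 45, 25, 5%), it reads 20% against 5%.

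**Size, organ level.** Scanning goes on until all organs are clear, so the result depends on how closely the organs clear together. In a simulation of 400,000 subjects (four organs, exponential clearance, median 2 months, no missed scans), the shares among scanned subjects at between-organ correlation 0, 0.5, 0.8 and 1 were:

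- 3 months, true 35%: 38, 44, 51 and 71%.
- 6 months, true 12.5%: 15, 19, 23 and 35%.

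The correlation-1 values check by hand: 0.354/0.5 = 71% and 0.125/0.354 = 35%. Across medians of 1 to 12 months, Weibull shapes 1 and 1.5, and correlations 0 to 1, the excess was 0 to 38 points at 3 months and 0 to 25 at 6 months. It is near zero at 3 months when organs clear independently at equal rates and slowly. Slow clearance alone does not remove it. For a shared clearance time with median 6 months, the 3-month share reads 0.707/0.794 = 89% against 71%; with median 12 months it reads 94% against 84%.

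**The level that section 4.9 asks about.** These figures use one threshold for stopping and for outcome. Scanning stops when nothing is detected, but the aim is satisfactory imaging. If that level is reached first, subjects already satisfactory are still being scanned and the excess shrinks. Suppose fully correlated exponential times with satisfactory imaging at median 2 months and no detectable signal at median 3. The 3-month share then reads 0.354/0.63 = 56%, not 71%, and the 6-month share 0.125/0.5 = 25%, not 35%.

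**Do the planned scans hold the answer?** Yes. In the table, counting stopped subjects as clear restores 25/50 and 10/50, the assumed true 50% and 20%. A harder test used 1,000 simulated trials of 50 subjects (median 2 months), with 15% of scans from month 1 missed at random and 20% of subjects re-dosed at random between 1 and 6 months. Time to clearance, treated as interval-censored, gave 35–36% at 3 months (true 35.4%, SD about 7 points) and 12–13% at 6 months (true 12.5%). Counting stopped subjects as clear and dropping missing visits gave 32–35% and 10–12%, slightly low.

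**The 1-to-3-month example.** If the 2-month scan were skipped, the shared-clearance 3-month share would read 0.354/0.707 = 50% in place of 71%. The 6-month share would not move, because the 3-month scan decides who is scanned at 6 months. Sections 4.7.1.5, 4.9 and 5.1.6.5 all list month 2, so the example is a loose illustration and does not set a different schedule.

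**The case for a change.** The case for a change is that a written rule costs a sentence or two and the direction of the error is certain. A descriptive percentage needs a denominator as much as a test does. Section 5.2 speaks of comparing time points, not of time to clearance, and section 8.3.2 lets analysis methods change without IRB approval, so nothing fixes the choice before the images are read. Re-dosing inside the 6-month window is foreseeable, since section 4.7.3 allows up to four study visits at least 30 days apart.

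The direction stands, and so does the observation that the rule is unstated. The rest does not make it a defect. Section 5.2 describes how images are read against baseline, not how subjects are tabulated. The reasons for absence can be told apart from the readings: a subject stopped for clearance has a last scan with nothing detected, while one who misses a scan or is re-dosed before clearing has a last scan that still shows ferumoxytol. Nor does stopping cut off the target, because a subject with no remaining signal change has already reached satisfactory imaging as far as ferumoxytol is concerned. The choice can therefore be made correctly when the results are written up. The acquired-only table is a mistake that an analyst would have to add to the plan.

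**Conclusion.** No change to the plan follows. The stopping rule is a fair trade-off, because it spares cleared subjects scans whose result can be inferred. The missing counting rule is detail that an analyst would fill sensibly, given that section 4.9 defines the aim as a duration.

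The error would arise only from a per-visit table restricted to acquired images, which no section plans. Its size is then illustrative: 0 to 25 points at 6 months and 0 to 38 at 3 months for an undetectable-signal endpoint, and probably less for the satisfactory-imaging level. At a 2-month median with correlation 0 or 0.5, the 6-month excess is about 3 or 6.5 points. For scale, the 95% interval for 6 of 50 is 6–24%.

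This rests on clearance being lasting after one dose and on assumed clearance curves. It concerns one secondary, descriptive objective in 50 subjects. The gap between 1 and 3 months in the example is a clerical slip.

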3.2 Secondary Objectives

3.2.1. This study will also provide preliminary, descriptive data for the following secondary objective: To localize ferumoxytol particles with histology and electron microscopy in biopsy samples from a small subset of subjects in which biopsy is needed. Results will also be compared to a companion study of brain tumor imaging entitled “NCI-Sponsored multi-disciplinary study for MR imaging of intravenous superparamagnetic crystalline particle ferumoxytol in primary high-grade brain tumors and/or cerebral metastases

3.2.2. To assess side effects/safety of ferumoxytol when given during MRI.

3.2.3 To assess the time course of iron uptake and clearance (of the first ferumoxytol injection) in abdominal organs, such as the liver, spleen, pancreas and bone marrow by applying usual abdominal MR sequences at multiple time points (up to 6 months) after ferumoxytol injection in a subgroup of subjects. For this purpose a subgroup of 50 subjects will be recruited from primary groups 1, 2 and 3.

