4.7.3 Study Duration

Study duration is 2 years. If there are no adverse events, the already enrolled subjects may repeat the study visit (days 1, 2, 3 and 4). This may be repeated at least 30 days apart, for up to a total of 4 study visits. Laboratory testing (creatinine/GFR) to check kidney function (prior to GBCA on study) and a pregnancy test in women of child bearing potential will be done at each subsequent visit.

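### Subgroup subjects given more ferumoxytol are removed from the clearance follow-up with no rule for their data: dropping them would make clearance look faster, and no scan before the new dose is secured

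*Combined protocol and SAP*

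**What the plan says.** The secondary objective in section 3.2 is "To assess the time course of iron uptake and clearance (of the first ferumoxytol injection) in abdominal organs", followed for up to 6 months in a subgroup of 50. Section 4.9 frames it as a time: how long until organ signal again allows satisfactory clinical imaging.

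Four rules bear on who is observed and for how long:

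- **Schedule.** Section 4.9 lists scans before, shortly after, 24-48 hours after, and then "1 week after, 1, 2, 3 and 6 months after ferumoxytol administration". Sections 4.7.1.5 and 5.1.6.5 give the same late time points.
- **Stopping.** Section 4.7.1.5: "Once no ferumoxytol is detected on the abdominal MR images, no further scanning will be done". Section 4.9 agrees: "Once signal changes are no longer present, subsequent imaging will not be necessary".
- **Repeat dosing.** Section 4.7.3, on repeating the study visit: "This may be repeated at least 30 days apart, for up to a total of 4 study visits".
- **Removal.** Section 4.7.1.5: "During this time, subjects that receive additional ferumoxytol will be removed from the subgroup portion of the study".

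On analysis, section 5.2 says only that images at the various time points are compared with baseline. Section 6.1 promises descriptive summaries and does not name the clearance subgroup. Neither gives an estimator, a denominator or a censoring rule.

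**The concern.** Re-dosing is permitted during the months in which clearance of the first dose is being timed. A subject already clear has finished scanning and has a complete record. A subject still showing ferumoxytol who is re-dosed has an incomplete one. Slower clearers are also exposed to the chance of re-dosing for longer. Subjects whose follow-up is cut short are therefore not a random sample of the 50, and the plan does not say what becomes of them.

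The result at stake is the interval after which abdominal MR is usable again. Understating it would mislead anyone planning an abdominal scan after ferumoxytol.

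Two related gaps remain however *removed* is read. First, nothing requires an abdominal scan before the repeat injection, and the earliest repeat visit falls at about the time of the 1-month scan. Second, the stopping-rule example in section 4.7.1.5 reads "if ferumoxytol is detected at 1 month, 3 month abdominal scans will be performed", without mentioning the 2-month scan that the same section lists.

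**Working it through.** The plan has no figure to reproduce: the 50 is not derived, and no clearance or re-dosing rate is given. Every rate below is an assumption.

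**Inputs.** Late scans at 1, 2, 3 and 6 months (4.7.1.5, 4.9). Scanning stops at first non-detection. Re-dosing is possible from about 1 month (4.7.3). Assumed: true cumulative clearance of 20, 40, 60 and 85% at those visits, and 10% of subjects re-dosed per month, starting after the 1-month scan and unrelated to clearance.

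**Per 100 subjects:**

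- Seen to clear at 1 month: 20
- At 2 months: 20 × 0.90 = 18
- At 3 months: 20 × 0.90² = 16.2
- Left among those who would clear at 6 months: 25 × 0.90⁵ = 14.76
- Left among those not clear by 6 months: 15 × 0.90⁵ = 8.86
- Not re-dosed before clearance: 20 + 18 + 16.2 + 14.76 + 8.86 = 77.82, so 22.18 are removed (11.1 of 50)

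**Three-month clearance under each reading (true value 60%):**

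- *Subjects re-dosed before clearance are deleted:* 54.2/77.82 = 69.6%.
- *Censored at re-dosing (life table):* the chances of clearing among those at risk are 20/100, 18/72 = 25% and 16.2/48.6 = 33.3%. Then 1 − 0.80 × 0.75 × 0.667 = 60.0%.
- *Kept in the denominator as not clear:* 54.2/100 = 54.2%.
- *Every re-dosed subject deleted, clear or not:* each clearance class shrinks by the same factor, 0.90⁵, so 60.0%.
- *Proportion clear among those scanned at 3 months:* 16.2/48.6 = 33.3%. This is low because cleared subjects have stopped scanning. It is the same at every re-dosing rate, so removal is not its cause.

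**Three-month clearance if subjects re-dosed before clearance are deleted:**

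| Assumed true clearance at 1/2/3/6 months | 2% re-dosed per month | 5% | 10% | 20% |
|---|---|---|---|---|
| 20/40/60/85% | 61.9% | 64.8% | 69.6% | 78.8% |
| 5/15/30/60% | 31.6% | 34.1% | 38.7% | 49.6% |
| 50/70/85/95% | 86.1% | 87.7% | 90.0% | 93.9% |

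The smallest overstatement is 86.1 − 85 = 1.1 points and the largest is 49.6 − 30 = 19.6 points. Censoring returns the true value in every cell.

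**If re-dosing depends on clearance speed** (first curve; subjects not clear by 3 months re-dosed at a different rate from the rest):

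- Slow clearers 15% per month, others 5%: the life table gives 1 − 0.80 × (1 − 19/72) × (1 − 18.05/46.95) = 63.7%. Deletion gives 76.2%.
- Slow clearers 5%, others 15%: the life table gives 1 − 0.80 × (1 − 17/72) × (1 − 14.45/50.55) = 56.4%. Deletion gives 62.4%.

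Censoring is then about 4 points out in either direction.

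**The scan before re-dosing.** These sums assume the 1-month scan is obtained before any re-dosing. If the repeat injection comes first, the last usable scan of the first dose is the 1-week scan.

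**The worked example.** Followed literally, it would leave clearance between months 1 and 3 known only to within 2 months, rather than the 1 month that the listed schedule gives.

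**The case against.** Ending observation at a second dose suits the objective. The target is clearance of the first injection, and section 4.2 bars subjects with prior ferumoxytol from the subgroup. The removal sentence sits in a paragraph about who is scanned and when, so stopping further scans is at least as natural a reading as discarding those already taken. Stopping scans amounts to censoring, which the sums show to be unbiased under independence. This stands. A reader might infer that the plan as written makes clearance look too fast; the documents do not support that, because they nowhere say that earlier scans are deleted.

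A reader might also infer that removal applies only to slow clearers. That goes too far. The sentence literally covers any subgroup subject re-dosed during the window, including one already clear. A subject still positive at 1 month need not be slow: under the first assumed curve, 80% are. And because clearance concerns several organs, a removed subject may already be clear in some of them. What follows from the stopping rule is narrower: observation is cut short only in subjects still being scanned.

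Size is also a fair objection. With 50 subjects, the standard error of a 60% proportion is √(0.6 × 0.4/50) = 6.9 points, so the overstatements at 2% and 5% per month (1.9 and 4.8 points) lie within it. The objective is secondary, in a study that calls itself exploratory.

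The 1-month scan is scheduled, missed time points are tolerated, and a repeat visit offers a chance to scan before the day 2 injection. But an opportunity is not a requirement. The worked example does not state that the 2-month scan is skipped; it is loose drafting set against explicit schedules.

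What remains is that the plan permits analyses giving anything from 54.2% to 69.6% for the same true 60%, depending only on how re-dosed subjects are counted, and does not choose among them.

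**Conclusion.** The concern holds in conditional form. Repeat dosing can fall inside the clearance window, removal cuts off observation in subjects still showing ferumoxytol, and the plan has no rule for their data. Dropping subjects re-dosed before clearance would overstate 3-month clearance by about 1 to 20 points, over assumed true 3-month values of 30 to 85% and assumed independent re-dosing of 2 to 20% per month. Censoring at re-dosing removes that bias if re-dosing is unrelated to clearance speed, and leaves a smaller error if it is not. The actual size cannot be fixed from the documents.

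The unsecured scan before re-dosing is a real but smaller gap, mainly one of lost information. The worked example is a separate drafting point. None of this touches the primary objectives; it merits a change because it bears directly on a stated time-to-clearance aim and costs little.

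**What to change.** 1. In section 4.7.1.5, replace the removal sentence with wording to this effect: abdominal follow-up ends at the next ferumoxytol dose; all scans before that dose are kept; a subject not yet clear is censored at the last scan before it.
2. For subgroup subjects not yet clear, require the short abdominal set at the repeat visit before the injection, as section 4.7.1.1 already allows for the baseline set.
3. In section 6.1, name a life-table or interval-censored estimate of time to clearance, preferably by organ. Report the number of re-dosed subjects and the reasons for re-dosing, so that readers can judge whether it was related to clearance.
4. Reconcile the worked example in section 4.7.1.5 with the 2-month scan listed there and in sections 4.9 and 5.1.6.5.

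Items 1, 3 and 4 are wording only. Item 2 costs about 8 minutes (2 for setup plus 6 sequences at 1 minute each, section 5.1.6.5) for a subject already attending for MRI; the downside is a slightly longer session.

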
An independent Data Monitoring Committee met to review the clinical safety data for all Phase 3 studies in October 2005, February 2006, June 2006, October 2006, and March 2007, and they identified no safety concerns.

The dose of 510mg ferumoxytol has not been used in imaging studies before. The highest dose used was 4mg/kg (280mg for a 70kg patient). However 2 x 510mg dose was studied for iron replacement therapy in large number of patients without significant adverse effects. (Besarab et al 2007). If there is no history of iron over load, there is no need to screen for iron over load since 0.5 g will not hurt patients, even if they have asymptomatic iron over load. Phase 3 data by Besarab using two doses of 510 mg in a phase 3 trial showed no significant toxicity. A higher dose of ferumoxytol will result in a better contrast enhancement 24 hours after injection due to a higher plasma level.

2.6.2.2 **Post-Marketing Program**

Investigator's Brochure Released on February 15, 2018:

Since approval, AMAG has conducted two post-marketing clinical trials (Protocol Number FER-CKD-201 and AMAG-FER-CKD-401). FER-CKD-201 was a randomized, open-label trial that compared the safety and efficacy of ferumoxytol to iron sucrose for the treatment of IDA in CKD subjects either on or not on dialysis. In this trial, 162 patients were randomized in a 1:1 ratio to either ferumoxytol or iron sucrose. Ferumoxytol was administered as a 1.02 g course given as a regimen of 2 x 510 mg within 2 to 8 (5±3) days. The most common AEs among ferumoxytol treated subjects were nausea (7.5%) and muscle spasms (5.0%). Adverse events occurring in ≥2.0% of subjects treated with ferumoxytol included: nasopharyngitis, URI, headache, hyperkalemia, and cough (3.8%); peripheral edema, constipation, diarrhea, hypotension, hypoglycemia, and anemia (2.5%). There was only one ferumoxytol related SAE in the FER-CKD-201 study, 1 event of anaphylactic reaction in 1 subject occurred on the same day as the subject's first dose of ferumoxytol.

The AMAG-FER-CKD-401 study was an international Phase IV, randomized, open-label, active controlled multicenter trial of the safety and efficacy of ferumoxytol (2x510 mg) compared with IV iron sucrose (10x100 mg) in the treatment of iron deficiency anemia in 293 patients with CKD on hemodialysis. Overall related AEs, related SAEs and protocol-defined AEs of special interest were reported 4.4%, 0% and 17.4%.

Imaging Program:

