3 OBJECTIVES

3.1 Primary objectives

3.1.1 Group 1: To compare ferumoxytol MR with gadolinium “gold standard” enhanced MR in adults with dural, parenchymal based, demyelinating or vascular CNS disease. This will involve imaging of the brain or the spine. Optimum sequencing parameters of ferumoxytol MRI will be established.

3.1.2 Group 2: To compare ferumoxytol MR with gadolinium enhanced MR in adults with any of the following (alone or in combination): vasculopathy of carotids, aorta, arteries of the extremities; or thrombosis of intraabdominal, pelvic or extremity veins. This will include carotid and/or aortic and/or extremity MRA or MRV as well as high resolution carotid plaque and vessel wall imaging and analysis. Optimum sequencing parameters of ferumoxytol MRI will be established.

3.1.3 Group 3: To compare ferumoxytol MR with gadolinium enhanced MR in adults with cervical lymphadenopathy, to identify imaging characteristics of the various etiologies (e.g. reactive vs. metastatic lymph nodes). Optimum sequencing parameters of ferumoxytol MRI will be established.

3.1.4 To assess the utility of ferumoxytol in subjects with renal disease, or with an allergy to gadolinium, who should not receive gadolinium-based contrast agents: this includes those with a chronic GFR < 50 ml/min/1.73m², acute kidney injury, and prior renal or liver transplant.

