4.2 Exclusion criteria

4.2.1 Subjects with clinically significant signs of uncal herniation, such as acute pupillary enlargement, rapidly developing motor changes (over hours), or rapidly decreasing level of consciousness.

4.2.2 Subjects who have a contraindication for MRI: metal in their bodies (a cardiac pacemaker or other incompatible device).

- 4.2.3 Subjects with known allergic or hypersensitivity reactions to parenteral iron, parenteral dextran, parenteral iron-dextran, or parenteral iron-polysaccharide preparations (Investigator's Drug Brochure, Combidex 2002; Advanced Magnetics Inc; Investigator's Drug Brochure, Code 7228; 2003 Advanced Magnetics Inc).
- 4.2.4 Subjects with known hepatic insufficiency or cirrhosis
- 4.2.5 Subjects with known or suspected iron overload (genetic hemochromatosis or history of multiple transfusions)
- 4.2.6 Subjects with symptoms or signs of hemodynamic instability.
- 4.2.7 HIV-positive patients on combination antiretroviral therapy are ineligible because of the potential for pharmacokinetic interactions with ferumoxytol.
- 4.2.8 Pregnant or lactating women are excluded from this study because of possible risk to the fetus or infant.
- 4.2.9 Subjects with three or more drug allergies from separate drug classes.
- 4.2.10 Subgroup only exclusion criteria: prior administration of ferumoxytol.

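### In the 6-month clearance follow-up, other parenteral iron or red cells given after the study dose are neither recorded nor censored, and can be read as retained ferumoxytol

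*Combined protocol and SAP*

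**What the plan says.** Secondary objective 3.2.3 is the time course of iron uptake and clearance after the first ferumoxytol injection, in a subgroup of 50. Section 4.9 defines the target as the time until organ signal "returns to a level which allows clinically satisfactory MR imaging of these organs". Section 5.2 reads each time point against the scan taken before ferumoxytol. Late scans are at 1, 2, 3 and 6 months, and scanning stops once ferumoxytol is no longer seen (4.7.1.5).

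Iron from other sources is considered at entry:

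- Section 4.2.5 excludes all subjects with "known or suspected iron overload (genetic hemochromatosis or history of multiple transfusions").
- Section 4.9 describes who does not enter the abdominal part in terms of iron generally: "If a subject does not qualify for the abdominal imaging (because of previous iron injection").
- Section 4.2.10 is narrower: "Subgroup only exclusion criteria: prior administration of ferumoxytol".

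After dosing, the only iron rule is in 4.7.1.5: "subjects that receive additional ferumoxytol will be removed from the subgroup portion of the study". The data list in 4.7.5 has no item for other iron or transfusion. The early-termination list in 8.3.4 allows withdrawal at discretion but does not mention iron.

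**The concern.** The objective concerns iron from one known injection, but the measurement is a signal change that any iron affecting the same organs could contribute to. The baseline scan can show iron that was already there. It cannot show iron given in month 2. Only a rule or a record during follow-up can separate the two, and the plan has one for ferumoxytol alone.

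The plan accepts the principle elsewhere. It removes subjects for repeat ferumoxytol, so later iron is taken to confound clearance. Section 4.9 treats earlier iron as a bar to entry, and 4.2.5 treats repeated transfusion as a source of iron overload. Section 5.2.1 plans a stain to tell ferumoxytol from blood-derived iron, but only in tissue; the abdominal MRI has no counterpart.

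Exposure is possible in the intended population. A primary objective is "To assess the utility of ferumoxytol in subjects with renal disease, or with an allergy to gadolinium" (3.1.4), and section 2.6.2 describes intravenous iron replacement in chronic kidney disease. Some subjects will have surgery (4.7.2), where transfusion may occur.

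At stake is the answer the subgroup is meant to give: how long after ferumoxytol abdominal MRI is again usable. If dates of other iron are not collected, an affected subject cannot be identified afterwards.

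**Working it through.** **Is the exposure caught anywhere?** Four places could catch it.

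| Place | When it acts | Catches other iron after the study dose? |
|---|---|---|
| 4.2.5, 4.2.10, 4.9 | At entry | No |
| 4.7.1.5 removal rule | During follow-up | Repeat ferumoxytol only |
| 4.7.4 and 4.7.5 follow-up and data list | Contact at about 4 to 6 weeks; events related or possibly related to ferumoxytol | No |
| 8.3.4 early termination | Any time, by discretion | No iron criterion, and no question asked that would prompt it |

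**Inputs for size.** From the documents: n = 50; scans at 1, 2, 3 and 6 months; scanning ends when a subject is read as clear. Assumed, because the documents give no value: the share c of subjects who receive other iron or red cells within 6 months, taken as 5%, 10% and 20%. Also assumed: the added iron shifts signal in the same direction as ferumoxytol and lasts through month 6. The plan states no clearance rate and no derivation of n = 50, so there is no figure of its own to reproduce.

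**Expected number exposed** = 50 × c: 2.5, 5 and 10 subjects.

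**Upper bound.** If every exposed subject is exposed before clearing and is misread, the observed cleared share is p × (1 − c) and the shift is p × c. With p = 100% the shift is 5, 10 and 20 points, which is the ceiling. With p = 80%:

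- c = 5%: 0.80 × 0.95 = 76%
- c = 10%: 0.80 × 0.90 = 72%
- c = 20%: 0.80 × 0.80 = 64%

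**With timing allowed for.** Iron given after a subject is read as clear does nothing, because scanning has stopped. Assume iron is given at a uniform time over 0 to 6 months, and that 10%, 20%, 40% and 20% of subjects first read clear at months 1, 2, 3 and 6, with 10% not clear by then. A subject who would clear at month t is affected with probability c × t/6.

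- Loss by month 3 = c × (0.10 × 1/6 + 0.20 × 2/6 + 0.40 × 3/6) = 0.283c, that is 1.4, 2.8 and 5.7 points off 70%.
- Loss by month 6 = 0.283c + c × 0.20 × 6/6 = 0.483c, that is 2.4, 4.8 and 9.7 points off 90%.

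A simulation under the same assumptions gives 68.5%, 67.3% and 64.4% at month 3, and 87.5%, 85.2% and 80.3% at month 6, in agreement.

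**Sampling error for comparison.** The 95% half-width is 1.96 × √(p(1 − p)/50). At p = 80% it is 1.96 × √(0.16/50) = 11.1 points. At p = 90% it is 1.96 × √(0.09/50) = 8.3 points.

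**The case against.** The case against is mainly about certainty and size, and much of it stands.

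- A reader might infer that other iron will be read as ferumoxytol and that the scan-stopping rule then never triggers. The documents do not support that. Three conditions must hold: the subject receives other iron, receives it before being read as clear, and its effect on signal is visible and lasting.
- A reader might set the iron sucrose course cited in section 2.6.2 (10 × 100 mg = 1,000 mg) against the 510 mg maximum study dose and infer about twice the confounding. That compares milligrams, not MR signal. The course was the comparator in a haemodialysis trial, and the documents give no signal effect for iron sucrose or red cells.
- The subgroup is not selected for renal disease. It draws on three groups capped at 260, 25 and 10, so Group 1 may supply up to 260/295 = 88% of those eligible. The entry rules also keep out some likely recipients, although 4.2.10 and 4.9 differ on which earlier iron counts, and 4.9 may only be a loose restatement of 4.2.10.
- Section 4.2.5 concerns repeated transfusion as a marker of overload. It does not show that one transfusion changes organ signal.
- Clearance is a secondary objective with descriptive summaries in an exploratory study. The removal rule already covers the one repeat iron exposure that the protocol itself creates.

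These points lower the likely size but do not close the gap. Entry rules cannot act on iron given later, and discretionary withdrawal cannot act on an exposure that no one asks about. Sampling error is not a full answer either: it has no direction, whereas under the stated signal assumption this error always points to slower clearance.

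**Conclusion.** The gap is real: during follow-up the rule is narrower than the plan's own treatment of iron at entry, and followed exactly it can bias clearance toward slower values. The documents do not show that it will. The range of 5 to 20 points is a ceiling, resting on an assumed exposure of 5% to 20% and on every exposed subject being misread and otherwise cleared; it should not be taken as an expected bias. With timing allowed for, the illustration gives about 1 to 6 points at month 3 and 2 to 10 points at month 6. At 5% or 10% exposure these shifts are below the sampling half-width (8.3 points at 90% cleared, 11.1 at 80%). At 20% exposure the month-6 shift of 9.7 points slightly exceeds the 8.3-point half-width at 90%. This is a modest defect in a secondary, descriptive objective. It is worth correcting because the remedy is cheap and the missing dates may not be recoverable later.

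**What to change.** At each abdominal visit, ask about any parenteral iron or red-cell transfusion since the study dose, and record its type and date. Keep all scans up to the first such date. Censor the main clearance summary there: the subject leaves the denominator for later time points, or is censored at the last earlier scan if time to clearance is reported. Add a sensitivity analysis that includes the later scans, and report how many subjects were exposed and when. Leave the existing rule on additional ferumoxytol as it is, and reconcile 4.2.10 with 4.9 on which earlier iron disqualifies a subject. None of this alters treatment.

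The cost is one question per visit and a few later scans left out of the main summary. Censoring also assumes that exposed subjects would have cleared like the others. If they would not, for example because renal patients both receive more iron and clear differently, the main summary is affected. That is why both analyses should be shown.
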